Prior to reinitiation, the Investigator will need to confirm that the benefit of reinitiating treatment outweighs any risk involved, such as that which led to initial treatment discontinuation. For participants with only SD at the time of discontinuation, the Investigator should confirm that no other reasonable treatment options are available. In addition, to be eligible for reinitiation, the participant must not have previously withdrawn consent for this study and should have been followed up with regular eCRF documented evaluation scans up to reinitiation of treatment.

A new baseline scan must be performed prior to reinitiation of study intervention. Additionally, relevant safety laboratory assessments, including both full hematology and full chemistry results within 2 weeks, must be available and verified. The clinical Investigator will determine whether additional evaluation and work-up are required on a case-by-case basis. A discussion with the study team is warranted to determine whether PK/biomarker testing is indicated upon restarting treatment.

7.1.3

Treatment Beyond Progression

7.1.3.1

Treatment Beyond Initial Progression

Participants will receive bintrafusp alfa as outlined in the Schedule of Activities until disease progression. Bintrafusp alfa may continue past the initial determination of disease progression according to RECIST v1.1 as long as the following criteria are met:

- Treatment with bintrafusp alfa is ongoing.
- No new unacceptable treatment or disease-related toxicity.
- Tolerance of study interventions.
- At least stable ECOG PS.
- Treatment beyond progression will not delay an imminent intervention to prevent serious complications of disease progression (e.g., CNS metastases).

A radiographic assessment should be performed within 4 to 6 weeks of original PD to determine whether there has been a decrease in the tumor size, or continued PD. The assessment of clinical benefit should be balanced by clinical judgment as to whether the participant is clinically deteriorating and unlikely to receive any benefit from continued treatment with bintrafusp alfa.

7.1.3.2

Treatment Beyond Confirmed Progression

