8.3 Adverse Events and Serious Adverse Events

The definitions of an AE and a SAE are in [Appendix 4](#).

8.3.1 Time Period and Frequency for Collecting Adverse Event and Serious Adverse Event Information

The AE reporting period for safety surveillance begins when the participant is initially included in the study (date of first signature of informed consent/date of first signature of first informed consent) and continues until the 28-day Safety Follow-up Visit, defined as 28 days (\pm 5 days) after the last study intervention administration. After this visit, all SAEs and nonserious

treatment-related AEs should be documented until the last Safety Follow-up Visit, defined as 12 weeks (\pm 2 weeks) after the last study intervention. Ongoing events at the 12-week Safety Follow-up Visit should continue to be monitored and documented until resolution or resolution with sequelae, unless the participant is documented as “lost to follow-up”.

During Prescreening, only AEs associated with study procedures should be recorded.

Any SAE assessed as related to study intervention must be recorded and reported, as indicated in [Appendix 4](#), whenever it occurs, irrespective of the time elapsed since the last administration of study intervention.

The method of recording, evaluating, and assessing causality of AEs (including SAEs) and the procedures for completing and transmitting SAE reports are in [Appendix 4](#).

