9.7 Time Window

Not applicable.

9.8

Definition of On-treatment Period

The on-treatment period is defined as the time from the first study intervention administration to the last study intervention administration date + 30 days, or the cut-off date or death or the earliest date of subsequent anticancer drug therapy minus 1 day, whichever occurs first, unless otherwise stated.

For participants with treatment ongoing at cut-off date, all data from the first study intervention up to the cut-off date will be considered under the on-treatment period.

Any systemic anticancer therapy, any anticancer surgery and any anticancer radiotherapy as documented in the 'Anti-cancer treatment after discontinuation details', 'Radiotherapy after discontinuation' and 'Surgery after discontinuation' eCRF pages will be considered as subsequent anticancer therapy.

The on-treatment period will include the initial treatment period as well as the reinitiation of treatment period, as applicable. Whether the participant reinitiates treatment (following the rules as outlined in the protocol) or not, the on-treatment period is defined as the time from the first study intervention administration to the last study intervention administration date + 30 days or the earliest date of subsequent anticancer drug (anticancer therapy, anticancer surgery and anticancer radiotherapy) therapy minus 1 day, whichever occurs first, unless otherwise stated.

For immune-related AEs as listed in section 15.2.3.2, an expanded on-treatment period will be used as a default for any analysis, defined as follows:

Time from the first study intervention to the last study intervention date + 90 days, death OR to the earliest date of subsequent anticancer therapy minus 1 day, whichever occurs first, unless otherwise stated.

9.9

Imputation of Missing Data

Unless otherwise specified all data will be evaluated as observed, and no imputation method for missing values will be used.

In all participant data listings, imputed values will be presented, and imputed information will be flagged.

Missing statistics, e.g. when they cannot be calculated, should be presented as 'nd' for 'not determined'. For example, if n = 1, the measure of variability (StD) cannot be computed and should be presented as 'nd'.

The following table for imputation rules for incomplete dates is to be considered:

Table 3 Imputation Rules for Incomplete Dates

Item	Imputation rules

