15.1 Adverse Events

Treatment-emergent adverse events (TEAEs) are those events with onset dates occurring during the on-treatment period or if the worsening of an event is during the on-treatment period (see on-treatment definition in section 9.8).

Changes in toxicity grade, seriousness or outcome of AEs are recorded as separate entries in the eCRF. Such entries reporting the same event in such immediately consecutive periods will be considered as one event in the analysis (using the field “AE id for new grade” in the eCRF). These events will be kept as separate records in the database in order to maintain the full detailed history of the events. The start date of the initial record in the sequence is taken as start date of the entire event, similarly the end date of the last event in the sequence is taken as end date of the entire event. The overall outcome of the adverse event is the outcome of the last event in the sequence. Duration of the AE and the TEAE flag will be adjusted accordingly in the analysis.

Incomplete AE-related dates will be handled as stated in section 9.9.

Related Adverse Events are those events with relationship to study treatment (as recorded on the “Adverse Events Details” eCRF page, Relationship with Bintrafusp alfa= Related) reported by the Investigator and those of missing or unknown relationship.

Serious Adverse Events (SAE) are those events reported on the “Adverse Events Details” eCRF page, with the “Serious Adverse Event” field ticked “Yes”.

Adverse Events Leading to Temporary Discontinuation are those events leading to temporary discontinuation of study treatment (answer to the question “Action(s) taken with Bintrafusp alfa” = “Drug interrupted” on “Adverse Event Details” eCRF page).

Adverse Events leading to Permanent Treatment Discontinuation are those events leading to permanent discontinuation of study treatment (answer to the question “Action(s) taken with Bintrafusp alfa” = “Drug withdrawn” on “Adverse Event Details” eCRF page).

Adverse Events leading to Death are those events leading to death (as recorded on the “Adverse Event Details” eCRF page, change in grade = “No” and outcome = “Fatal”, or Grade = “Grade 5 or death related to AE” or Serious adverse event = “Yes” and seriousness criteria include “Results in death”).

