Adverse Events of Special Interest (AESI): AESI are identified according to a pre-specified search list of MedDRA Preferred Terms (PTs) which will be finalized before the database lock. Categories of AESI include:

- Infusion-Related Reactions (IRRs)
- Immune-Related Adverse Events (irAEs)
- Skin AEs possibly related to TGF- β inhibition
- Anemia

Bleeding events are those events belonging to the MedDRA SMQ Haemorrhage terms (excluding laboratory terms).

All analyses described in this section will be based on TEAEs if not otherwise specified. The AE listings will include all AEs. AEs outside the on-treatment period (prior or after) will be flagged in listings. AE occurring during the reinitiation phase will be considered as TEAE and will be reported in the summary tables and will be flagged in the listings.

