15.2 Deaths, Other Serious Adverse Events, and Other Significant Adverse Events

15.2.1 Deaths

All deaths, deaths within 30 days after last dose of study treatment (in case of reinitiated participants, the last dose will be the last dose of the reinitiation phase), death within 60 days after first dose of study treatment (for all participants, the first dose will be the first dose of the first treatment phase) as well as the primary reason for death will be tabulated based on information from the “Death” eCRF pages.

The following summaries will be provided:

- Number of deaths (including deaths during reinitiation phase)
- Number of deaths within 30 days after last dose of study treatment
- Number of deaths within 60 days after first dose of study treatment
- Primary Reason for Death
 - Progressive disease and/or disease related condition
 - Event unrelated to study treatment
 - Event related to study treatment
 - Unknown

In addition, date and cause of death will be provided in an individual participant data listing together with following dosing information: participant identifier, age, sex, race, date of first/last study intervention, number of infusions, day relative to the first and the last infusion, primary reason, autopsy (Y/N/U), AEs with fatal outcome (list PTs of AEs with outcome = Fatal, as well as grade 5 or serious resulting in death), flag for death within 30 days of last dose of study treatment and flag for death within 60 days of first dose of study treatment.

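### For participants who reinitiate treatment, SAP 9.8 sets one on-treatment window across both courses: it takes in the off-drug gap and, if anticancer therapy is given in the gap, leaves out course 2.

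*SAP*

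**What the plan says.** SAP 9.8 opens its reinitiation paragraph with the statement "The on-treatment period will include the initial treatment period as well as the reinitiation of treatment period, as applicable". The next sentence gives the rule: "Whether the participant reinitiates treatment (following the rules as outlined in the protocol) or not, the on-treatment period is defined as the time", with the start at initial dosing. The end is whichever comes first of two dates, the second of them less one day: "the last study intervention administration date + 30 days or the earliest date of subsequent anticancer drug (anticancer therapy, anticancer surgery and anticancer radiotherapy) therapy". The opening paragraph of 9.8 also ends the period at death or data cut-off. For irAEs the same single interval runs to last dose + 90 days.

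SAP 15.2.1 fixes which dose is the last one: "in case of reinitiated participants, the last dose will be the last dose of the reinitiation phase".

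Several outputs use this period:

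- SAP 15.1: TEAEs, it says, "are those events with onset dates occurring during the on-treatment period or if the worsening of an event is during the on-treatment period". It adds that "AE occurring during the reinitiation phase will be considered as TEAE and will be reported in the summary tables".
- SAP 15.3: worst on-treatment grade, shift from baseline and the liver function categories. Under SAP 9.2, baseline is the last value before the first dose of course 1.
- SAP 15.1.1: AEs that start or worsen after the on-treatment period go into a separate listing.

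Protocol 9.4.2 leaves reinitiation data to the analysis plan, so nothing there overrides SAP 9.8.

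**The concern.** Protocol 7.1.2.1 allows one further course after progression off therapy, or after an AE that led to discontinuation has been managed or has resolved. Its only time limit is the end of the study, so the gap can be long. A single interval treats the whole gap as on-treatment.

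Three things follow:

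- Two participants with the same AE at the same time after course 1 are classified differently because of a decision taken after the AE began.
- Laboratory values obtained to decide on course 2 are counted as results on treatment.
- The cut at subsequent anticancer therapy acts on the single interval, so it can end the period before course 2 starts and exclude events that did occur on drug.

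At stake is the TEAE classification behind the secondary safety endpoint, and the on-treatment status of laboratory values.

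**Working it through.** The plan states no figure on this point, so there is none to reproduce. The check sets the rules side by side and then does the date arithmetic.

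**1. A gap AE.** Take an AE starting 10 weeks (70 days) after the last dose of course 1.
- No reinitiation: the period ended at day 30, so the AE is post-treatment.
- Reinitiation later, with no anticancer therapy before the AE: the last dose is now that of course 2, the AE lies inside the interval, and it is a TEAE.

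**2. Laboratory values in the gap.** Protocol 7.1.2.1 requires before course 2 that "relevant safety laboratory assessments, including both full hematology and full chemistry results within 2 weeks, must be available and verified". With a gap of G days, the earliest such sample is at day G − 14 after course 1. It falls beyond day 30 whenever G − 14 > 30, that is, G > 44. Under 9.8 it then enters the worst on-treatment grade, shift and liver categories. Scheduled hematology and biochemistry stop at the 28-day visit (Protocol Table 1), so these are the main laboratory values affected.

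**3. Length of the window.** All course and gap lengths here are assumptions; the documents give none. Let course 1 run 168 days and course 2 run 84 days from first to last dose, let G be the days from last dose of course 1 to first dose of course 2, and assume no other anticancer therapy.
- SAP 9.8: 168 + G + 84 + 30 = 282 + G.
- Two course windows (G ≥ 30): (168 + 30) + (84 + 30) = 312.
- Excess: (282 + G) − 312 = G − 30. For irAEs the excess is G − 90, or 0 if G is 90 or less.

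| G (assumed) | SAP 9.8 window | Two windows | Off-drug days beyond +30 | irAE: beyond +90 |
|---|---|---|---|---|
| 60 | 342 | 312 | 30 | 0 |
| 90 | 372 | 312 | 60 | 0 |
| 180 | 462 | 312 | 150 | 90 |
| 365 | 647 | 312 | 335 | 275 |

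At G = 180 the ratio is 462/312 = 1.48. The excess depends only on G, not on course length. Counting whole calendar days strictly inside the gap lowers each non-zero excess by one.

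**4. What is collected in those days.** Protocol 8.3.1 collects all AEs to the 28-day visit. "After this visit, all SAEs and nonserious" treatment-related AEs are then documented to 12 weeks, and related SAEs at any time. Of the 150 extra days at G = 180, days 31 to 84 (54 days) have restricted collection and days 85 to 180 (96 days) require related SAEs only. The 96 rests on 8.3.1; the Schedule of Activities also marks AE documentation at Long-term Follow-up.

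**5. Anticancer therapy in the gap.** Protocol 7.1.2.1 does not exclude it. If it starts on day T after course 1, with T before course 2, the 9.8 period ends at day T − 1. None of the 84 + 30 = 114 days of the course 2 window is then on-treatment. Under the 15.1 definition course 2 AEs are not TEAEs; under the later statement in 15.1 they are.

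**6. Which therapy cuts the period.** SAP 9.8 counts systemic therapy, surgery and radiotherapy. SAP 12.4 uses the start of new drug therapy only, as does Protocol 9.4.2. Radiotherapy in the gap therefore closes the period under one section and not under the other.

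**The case against.** The best defense is that 9.8 is a deliberate, over-inclusive safety convention. It says the period will include both courses, not that it consists only of them, and 15.2.1 picks the last dose in the same way. That stands: the two sentences in 9.8 do not contradict each other, and counting the gap is by itself a choice of convention. It does not answer the dependence on a later decision, nor the conflict with 15.1, where the rule under-includes.

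The listings also help. They show the day relative to the most recent infusion before onset, flag reinitiation-phase AEs, and give all AEs of reinitiated participants separately (SAP 15.1.1). A careful reader could recover a gap AE. It would still carry a TEAE flag and be absent from the listing of post-treatment AEs, and no flag marks the gap.

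Three stronger readings are tempting but unsupported:

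- **ECOG shift.** A reader might infer that off-drug ECOG scores distort it as well. ECOG PS is scheduled at treatment visits, End-of-Treatment and the 28-day (±5) visit, so no scheduled score falls in the gap beyond about day 33.
- **Attribution.** A reader might infer that gap findings are attributed to bintrafusp alfa. TEAE status is temporal; related TEAEs are tabulated separately, using the Investigator's assessment.
- **Incidence.** A reader might size the effect as one participant in 29. That is the planned number; SAP 4.1 records early discontinuation with few participants. A gap event also changes an incidence only if that participant had no such event on drug.

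**Conclusion.** The point holds as a defect in the window definition. Read literally, 9.8 classifies off-drug AEs as TEAEs only in participants who later reinitiate, counts pre-reinitiation laboratory values as on-treatment, and can exclude course 2 events that 15.1 calls TEAEs. The excess is G − 30 days for a gap of G days (G − 90 for irAEs, if positive). The 462 against 312 day comparison illustrates this under assumed lengths; it does not estimate what happened in the trial.

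Practical impact is probably small. The number of reinitiators is not stated and may be zero, in which case nothing changes. Only events actually collected in the gap can be misclassified. SAP 4.1 replaces summary tables with listings as deemed appropriate, so the effect is mainly on TEAE and on-treatment flags. A reader might conclude that the safety results as a whole are biased; the documents do not support that.

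**What to change.** First check whether anyone reinitiated. If nobody did, one sentence in the study report closes the point. Otherwise amend SAP 9.8:

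- Define the on-treatment period as the union of two windows, each from first to last dose of its course + 30 days (+ 90 for irAEs).
- Cut each window at death, data cut-off or the day before subsequent anticancer therapy started after that course. This also removes the conflict with 15.1.
- Use one definition of subsequent anticancer therapy for the on-treatment period in 9.8 and 12.4.
- Report gap AEs with the post-treatment AEs, and leave gap laboratory values out of the worst on-treatment, shift and liver derivations.

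The cost is a wording change, one extra pair of dates per reinitiated participant and some additional programming; reinitiation records are already identified in the data. The change does not supply a separate baseline for course 2. Shifts would still be measured from before course 1, and the report should say so.

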9.10 Scoring of HRQOL Data

Not applicable.

9.11 Further Specifications

Table 7 **Further specifications**

Re-screened participants	Re-screened participants will be only counted once in the screening analysis set, considering the latest screening (screening with latest informed consent).
Data collected after reinitiated treatment	Data collected after reinitiation of treatment will be included in the summary statistics. A data listing will include AE data for all reinitiated patients.
Preferred term for analysis of WHO-DD coded data	For data coded according to WHO Drug B3 (e.g., concomitant medications), summaries will be done on the preferred term level where the preferred term is corresponding to codes ending in 01001. With this approach, variations of salt forms of active ingredients will be analyzed under the same term, e.g. diphenhydramine and diphenhydramine hydrochloride will be analyzed as the same preferred term diphenhydramine.
Categorization of participant for COVID-19 impact assessment	For the assessment of COVID-19 impact on this study, participants will be categorized as being potentially affected by COVID-19 based on the COVID-19 pandemic start date, defined as the minimum of the first COVID-19 death date per country and 11 March 2020 (WHO-start of world-wide pandemic). First death from COVID-19 occurred per country is determined according to the published data by European Centre for Disease Prevention and Control (status of 26 th June 2020).

WHO-DD: World health organization drug dictionary.

9.11.1 Unscheduled Assessments

As per database definition, the safety unscheduled assessments are always linked to a scheduled timepoint (each unscheduled assessment is linked to the previous scheduled timepoint). Safety data retrieved from an unscheduled timepoint (vital signs, ECG and laboratory data) will be analyzed according to the following scenario:

- For shift table, they will be taken into account in the definition of the worst assessment during study.
- For description at each timepoint post-baseline, the first available result (in chronological order) per timepoint will be taken into account in the analysis in case of multiple values.
- For description at baseline, the last available result before first study intervention will be taken into account in the analysis in case of multiple values.

For immunogenicity analysis, unscheduled visits will also be taken into account in the analysis following the same rules as detailed above.

For PK analysis, unscheduled samples will not be linked to a scheduled timepoint and will be excluded from summaries.

10 Study Participants

The subsections in this section include specifications for reporting participant disposition and study treatment/study discontinuations. Additionally, procedures for reporting protocol deviations are provided.

10.1 Disposition of Participants and Discontinuations

The number and percentage of participants in each of the below disposition categories will be presented based on the data collected in the eCRF. Percentages will be presented with respect to the number of treated participants.

- Total number of prescreened participants
- Number of participants who did not continue beyond prescreening (overall and by reason)
- Total number of participants screened (i.e. participants who gave informed consent)
- Number of re-screened participants
- Number of participants who discontinued from the study prior to treatment overall and grouped by the main reason (e.g. the failed specific inclusion or exclusion criteria, progressive disease, adverse event, lost to follow-up, death, withdrawal of consent and other)
- Number of participants who received at least one dose of study intervention (FAS/SAF analysis set)

The end of treatment status will be summarized by:

- Number and percentage of participants with treatment ongoing at the data cut-off date
- Number and percentage of participants off study treatment, grouped by main reason (treatment completed as per protocol, progressive disease, death, adverse event, lost to follow-up, protocol non-compliance, withdrew consent, other)

With regards to treatment reinitiation status, it will be summarized by:

- Number and percentage of participants who reinitiated the study treatment
- Number and percentage of participants with treatment ongoing after reinitiation
- Number and percentage of participants who discontinued treatment after reinitiation

The end of study status will be summarized by:

- Number and percentage of participants with study ongoing at cut-off date (including participants with treatment ongoing and participants who are off treatment and in follow-up)
- Number and percentage of participants who completed/discontinued the study participation, with the associated main primary reason (study completed according to protocol, adverse event, lost to follow-up, protocol non-compliance, death, withdrew consent, other)

In addition, the number of participants screened, and enrolled in each analysis population defined in Section 8.1 will be summarized, overall and by region (North America and Europe), country within region and site.

A listing containing participant disposition information will be displayed, including all participants (i.e. including screening failures, but not re-screened participants (at their screen failure time) which will be listed in a specific listing). The listing will include the following information: participant identifier, date of informed consent, included in the study (if not reason for exclusion), first/last study intervention date, date and reason off-treatment, date and reason off-study, population flags. If the reason for exclusion from trial, off-treatment or off-study are categorized as “Other, specify” or “Withdrew consent from treatment, specify”, the verbatim text as entered in the eCRF will be presented in the listing. This listing will be sorted by participant ID.

In addition, a listing of participants for which study treatment has been reinitiated will be provided with the following information: participant identifier, date of first study intervention, date of last study intervention, reason for treatment termination, date of last reinitiation of study treatment administration date and status at end of treatment reinitiation including reason for treatment discontinuation, as applicable. If the status at end of treatment is categorized as “Other, display the verbatim text as entered in the eCRF. This listing will be sorted by participant ID.

If any re-screened participants are observed, they will be presented in a specific listing which will include: participant identifier (identifier at inclusion in the study), date of informed consent at inclusion, date of first study treatment administration, initial participant identifier (identifier at screen failure), date of informed consent at screen failure, date and reason of screen failure. Note in case participants have been screened several times, all screening attempts will be listed. This listing will be sorted by participant ID.

